Subsequent trough anti-Xa levels will be performed eight hours after the third dose. Repeat anti-Xa levels will be drawn eight hours after the third dose of the new regimen(s) (see attached figures) for patients in the treatment arms and eight hours after the sixth dose for those in the control arm. For patients in group 2, anti-Xa levels will be drawn within 30 minutes of the fourth and eighth doses. If patients continue to be subtherapeutic, the group 1 dose will be increased to 50 mg every 12 hours, while the group 2 dose will remain at 30 mg every eight hours. Group 2 will not have subsequent dose adjustment, as this regimen has not been previously evaluated. Coordinated AT-III and TEG will be performed with the first anti-Xa assessment and the first repeat assessment in the interventional groups. After the initial assessments, weekly anti-Xa and AT-III will be collected on patients requiring dose adjustment for up to 28 days. If the weekly trough anti-Xa level is ≥ 0.3 IU/mL, the enoxaparin dose will be decreased to the previous dose (i.e., enoxaparin 50 mg every 12 hours would be decreased to 40 mg every 12 hours; enoxaparin 40 mg every 12 hours would be decreased to 30 mg every 12 hours; enoxaparin 30 mg every eight hours would be decreased to 30 mg every 12 hours) with patient remaining in enrolled study group for all outcome analyses.

Randomization

Following informed consent, serum AT-III and anti-Xa values will be assayed per protocol. Patients with an anti-Xa level < 0.1 IU/mL undergo unblinded 1:1 randomization to ensure equal allocation to each intervention group. Randomization will be performed by study personnel. If the standard of care anti-Xa per trauma protocol is not collected or inappropriately drawn/mistimed by nursing or phlebotomy staff, patients will be able to have a repeat standard of care anti-Xa within 24 hours of initial draw for assignment to treatment or control groups for enrollment and outcome analysis (protocol amendment). This practice aligns with the current daily trauma protocol operations.

Data Collection:

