VTE are associated with a high morbidity and mortality. Optimal LMWH dosing has not been established for critically injured patients who have altered pharmacokinetics due to altered volume of distribution and metabolism, variable age and weight, and potential decreases in AT-III. Subtherapeutic serum anti-Xa trough concentration has been associated with increased risk for VTE. This pilot clinical investigation has the potential to revolutionize enoxaparin dosing and VTE prevention through anti-Xa guided dosing. Thorough evaluation of risk factors for reduced anti-Xa may provide a focused assessment of patients requiring anti-Xa assessment and subsequent dose adjustments. Overall, optimal enoxaparin dosing will result in fewer VTE events without increasing bleeding risk with an anti-Xa driven adjustment. Improved patient outcomes, expansion of scientific knowledge, and development of VTE prevention protocols may result.

Potential Risks, Discomforts, and Inconveniences

Level of Risk

VTE risks with inadequate prophylaxis have been previously justified above. Risks of increased enoxaparin doses include major and minor bleeding events. Risks will be mitigated by appropriate exclusion of patients with low body weight and increased serum creatinine / decreased creatinine clearance. Serum assays for risk of bioaccumulation will be performed weekly with subsequent dose reduction. Additionally, patient serum creatinine and creatinine clearance will be assessed daily by the trauma team with appropriate therapy modification should patient's renal function worsen. Patients with a 50% change in serum creatinine or an absolute change in serum creatinine by 1 mg/dL will be removed from the study. If these changes in renal function occur after patient has received initial laboratory assessment (i.e., anti-Xa; AT-III; TEG) will be included in the primary outcome analysis.

Blood volume loss due to serum anti-Xa, TEG, and AT-III assay as described above is minimal (2.7 mL x 2). Patients requiring peripheral vein access for serum assays will be at risk for pain/discomfort, bruising, fainting, and infection from phlebotomy sites.

Data Safety Monitoring Plan

Collected data will be screened for adverse events. [name] will act as medical monitor and review collected data and all adverse events to ensure patient safety.

Data Analysis

Primary Endpoints

1. Initial AT-III activity between the control group and the intervention group.

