Statistical analyses will be performed using SAS version 9.3 (SAS Institute, Inc., Cary, NC). An intention-to-treat model will be used for data analysis. Patients excluded due to change in renal function will be included in the primary outcome analysis, but not patient outcome analyses for VTE and bleeding outcomes. Nominal data will be reported using frequencies of occurrence and proportions as appropriate. Continuous data will be reported using means and standard deviations or medians and ranged as appropriate per distribution. Hypothesis testing for nominal data will be performed using the Fisher's exact test or chi square test as required based on sample size. Continuous data will be compared using student's t-test/ANOVA or rank sum/Kruskal-Wallis ANOVA for normally distributed and non-normally distributed data, respectively. A p-value < 0.05 will designate statistical significance. Time-to-event analyses will be compared as appropriate and presented as Kaplan-Meier curves. Multivariate logistic regression will be performed for low anti-Xa risk determination. All values with a p-value < 0.2 will be included in the model. Serum AT-III, weight, and age will be forced into the model, regardless of p-value.

A total of 200 patients will be enrolled. Assuming that 50% of patients will have an undetectable anti-Xa on enoxaparin 30 mg every 12 hours, we hypothesize the intervention group will have an absolute reduction in AT-III activity of 10% compared to the control group if the control group has a mean AT-III activity of 80% with a standard deviation of 25%. Secondly, we hypothesize that there will be an absolute difference of 27% in the proportion of patients who achieve goal anti-Xa between group 1 and group 2, assuming 50% of group 1 achieves goal. To achieve an 80% power with an alpha of 0.05 for both outcomes, goal enrollment is 200 patients (table 2).

Table 2. Power analysis for each outcome

AT-III activity difference between control and intervention			
Absolute difference in means	Standard Deviation		Sample Size
10%	25%		200
10%	30%		286
10%	10%		34
20%	30%		74
20%	10%		12
Anti-Xa ≥ 0.1 IU/mL attainment between group 1 and group 2			
Group 1 Proportion	Group 2 Proportion		Sample Size
50%	77%		100
50%	75%		116
60%	80%		164
80%	90%		398
70%	80%		588
VTE reduction between study groups			
Estimate Source	Control Proportion	Intervention Proportion	Sample Size
Malinoski ¹⁵	37%	11%	98

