- h. Patients with a RAP score ≥ 5 without enoxaparin initiated within 72 hours of admission
- i. Pregnancy
- j. Incarceration

Patients with a 50% change in serum creatinine or an absolute change in serum creatinine by 1 mg/dL after randomization will be removed from the study. If these changes in renal function occur after patient has received initial laboratory assessment (i.e., anti-Xa; AT-III; TEG), the patient will be included in the primary outcome analysis per intention-to-treat design.

Consenting process and plan

Patients will be identified as previously described per trauma service. Permission to consent per the trauma team attending will be obtained prior to administration of consent. Patients initiated on enoxaparin 30 mg every twelve hours prior per the trauma protocol who meet inclusion and exclusion criteria will be eligible for consent. Study personnel will administer in the patient's room. Informed consent will be obtained prior to first serum laboratory assay. The trauma team should alert research personnel as soon as possible for administration of informed consent. Patients will be able to be consented and enrolled up to four hours prior to the first serum laboratory assay. At-risk or vulnerable patients unable to give consent will have next of kin consented. Investigators will be available seven days a week and will

continue correspondence with subjects throughout the study and until hospital discharge (see “Informed Consent” form).

Compensation

Patients will not receive any direct compensation for research involvement.

Subject costs

[figure not shown]
There are no additional costs to subjects.

REFERENCES

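### The plan declares intention-to-treat but leaves patients with a creatinine change out of the VTE and bleeding analyses, and no planned analysis of those outcomes keeps them

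*Combined protocol and SAP*

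**What the plan says.** Five places in the combined protocol and SAP bear on who is analysed.

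- **Data Analysis, statistical paragraph.** "An intention-to-treat model will be used for data analysis", with no limit by endpoint. The next sentence says that patients excluded for a change in renal function "will be included in the primary outcome analysis, but not patient outcome analyses for VTE and bleeding outcomes".
- **Level of Risk.** "Patients with a 50% change in serum creatinine or an absolute change in serum creatinine by 1 mg/dL will be removed from the study". This follows a sentence saying that creatinine and clearance "will be assessed daily by the trauma team with appropriate therapy modification"; that sentence goes on to make the modification conditional on worsening renal function.
- **Exclusion Criteria, closing paragraph.** The same trigger, but with a time limit: patients with a 50% change or an "absolute change in serum creatinine by 1 mg/dL after randomization will be removed from the study". If the change comes after the initial laboratory assessment, "the patient will be included in the primary outcome analysis per intention-to-treat design".
- **Intervention.** A patient whose dose is lowered for a weekly trough of 0.3 IU/mL or more is handled "with patient remaining in enrolled study group for all outcome analyses".
- **Randomization.** Only patients with anti-Xa below 0.1 IU/mL "undergo unblinded 1:1 randomization to ensure equal allocation to each intervention group". Controls are not randomised.

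Secondary Endpoints lists VTE, major and minor bleeding, and transfusion for control versus intervention. Aim 2 in Purpose of Study compares the anti-Xa adjusted dosing strategies on VTE and bleeding, which brings in group 1 versus group 2.

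**The concern.** Intention-to-treat keeps each patient in the assigned group whatever happens later. Here a patient leaves the VTE and bleeding analyses because of something that happens after assignment, and that event is unlikely to be unrelated to outcome. Pharmacokinetic / Safety Information says that excluding patients with poor renal function lowers bleeding risk, because drug elimination is reduced in them. Level of Risk names bleeding as the hazard of higher doses and lists renal monitoring among the safeguards. On the protocol's own reasoning, triggered patients may differ in bleeding risk from the rest.

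The rule removes patients, not follow-up time. Read literally, a bleed or a VTE recorded before the creatinine change goes too. No section says so expressly, and none preserves such events.

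The total daily dose differs by design: 2 × 30 = 60 mg in controls, 2 × 40 = 80 mg in group 1 (2 × 50 = 100 mg after escalation) and 3 × 30 = 90 mg in group 2. It is therefore credible, though unproven, that the risk in triggered patients differs by group. At stake is aim 2, including the one randomised comparison in the trial.

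**Working it through.** **1. The plan's own figure.** No stated number is in dispute. The goal of 200 rests on AT-III and anti-Xa attainment, and it reproduces. For a 10-point difference and SD 25, n per group = 2 × (1.96 + 0.84)² × (25/10)² = 98, or 99 without rounding the normal quantiles, so 198 in total; the noncentral t gives 200. For 50% versus 77% the result is 98, against 100 in Table 2. The renal exclusion enters neither calculation.

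**2. Search for an analysis that keeps these patients.** Retention after a creatinine change is stated for the primary outcome only (Data Analysis, Level of Risk, Exclusion Criteria). The retention clause under Intervention covers dose decreases only. Kaplan-Meier curves are planned as appropriate, but are not tied to VTE or bleeding. The medical monitor's review of adverse events is monitoring, not a comparative analysis. Nothing censors these patients at the change, and no sensitivity analysis is planned.

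**3. Possible size for bleeding (all inputs are assumptions).** Let b = 5% be the risk in untriggered patients, f the fraction triggered, R the relative risk in triggered patients, and c the share of their bleeds that count. The share c matters because most bleeding definitions count only while the patient is on enoxaparin.

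All-patient rate = b × (1 + f(Rc − 1)). Analysed rate = b. Share of the group's bleeds dropped = fRc / (1 + f(Rc − 1)).

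| f | R | c | All-patient rate | Analysed | Share dropped |
|---|---|---|---|---|---|
| 0.05 | 2 | 1 | 5.25% | 5.0% | 9.5% |
| 0.10 | 3 | 1 | 6.0% | 5.0% | 25% |
| 0.20 | 4 | 1 | 8.0% | 5.0% | 50% |
| 0.05 | 2 | 0.5 | 5.0% | 5.0% | 5.0% |
| 0.10 | 3 | 0.5 | 5.25% | 5.0% | 14.3% |
| 0.20 | 4 | 0.5 | 6.0% | 5.0% | 33.3% |
| 0.10 | 2 | 0.25 | 4.75% | 5.0% | 5.3% |

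The last row shows that the sign can reverse: the gap runs from −0.25 to +3.0 points. For scale, the standard error of a 5% rate is √(0.05 × 0.95/100) = 2.2 points for 100 patients and √(0.05 × 0.95/50) = 3.1 points for 50. Most of these gaps are smaller than that; the 3.0-point gap exceeds the standard error at 100 patients.

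**4. Comparison between two groups.**
- Equal f, R and c in both groups: the true and the analysed risk ratios are both the ratio of the untriggered risks, so there is no bias.
- Rc = 2 in one group and 4 in the other: at f = 0.05, 0.10 and 0.20 the true ratios are 1.15/1.05 = 1.10, 1.30/1.10 = 1.18 and 1.60/1.20 = 1.33. Each is analysed as 1.00.
- Rc = 1 in one group and 0.5 in the other, f = 0.10: the true ratio is 0.95/1.00 = 0.95, again analysed as 1.00.
- Unequal trigger rates, 5% and 20%, with 6% risk in retained and 20% in excluded patients: 0.95 × 6% + 0.05 × 20% = 6.7% against 0.80 × 6% + 0.20 × 20% = 8.8%, analysed as 6% against 6%.

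**5. VTE.** Take the 5.5% registry rate in Table 2 for untriggered patients and f from 0.05 to 0.20. If triggered patients have half the risk, the all-patient rate is 5.36% to 4.95%. If they have twice the risk, it is 5.5% × 1.05 = 5.78% to 5.5% × 1.20 = 6.60%. Either is analysed as 5.5%. The documents do not say which holds.

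**6. The trigger.** Exclusion Criteria limits it to changes after randomisation; Level of Risk and Data Analysis do not. No reference creatinine is given. A rise is implied by the sentence about worsening function, and by Data Collection listing highest creatinine and lowest clearance, but the trigger itself speaks only of a change.

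**The case against.** The best defence is that the exclusion is pre-specified and stated in the sentence directly after the intention-to-treat declaration. It affects secondary endpoints of a pilot, and it names only VTE and bleeding, not transfusion or bioaccumulation. Three of the four VTE scenarios in Table 2 need 390 or more patients, against 200 planned. Secondary Endpoints lists VTE and bleeding only for control versus intervention, which is not a randomised contrast; group 1 versus group 2 rests on aim 2. All of that stands, and it limits the weight of the point. It does not supply an analysis that keeps these patients.

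Stronger readings are tempting, and the documents do not support them:

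- **That the departure is concealed.** It is disclosed.
- **That bleeding must be understated.** The on-enoxaparin limits in Secondary Endpoints mean that bleeds after the drug is stopped may not count, so the sign is open.
- **That VTE risk in triggered patients can be taken from the 14.4% versus 5.4% in the Background.** Those were dalteparin patients grouped by trough level, not by renal change.
- **That controls are exempt because they are not randomised.** One phrase in Exclusion Criteria allows this, but Level of Risk and Data Analysis have no such limit, and retention is tied to the initial laboratory assessment, which controls also have. The wording needs reconciling; it is not evidence of an exemption.
- **That the trigger has no direction at all.** Context points to a rise.
- **That the Intervention clause contradicts the exclusion.** It concerns dose reduction for a high trough only. It shows that the plan can keep patients in their group, not that it promised to do so here.

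**Conclusion.** The point holds and should be fixed. The plan declares intention-to-treat without limit, then removes whole patients from the VTE and bleeding analyses for a post-assignment event, and offers no analysis of those outcomes that retains them. In the strict sense intention-to-treat applies to group 1 versus group 2; for control versus intervention it can only mean analysis by enrolled group. Either comparison can be biased if the trigger rate, or the event risk in triggered patients, differs by group. With equal rates and risks the ratio is unaffected.

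Neither size nor direction can be derived from the documents for either outcome. The figures above rest on assumed trigger rates and risks; they show that the effect may be nil, may run either way, and is often within sampling error. The stated exclusion does not touch the primary endpoints or the sample size.

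**What to change.** 1. In Level of Risk, Data Analysis and Exclusion Criteria, separate stopping study treatment (a clinical decision, not judged here) from removal from analysis.
2. Analyse VTE and bleeding in all assigned patients, in their assigned group, through discharge or day 28, the window that Secondary Endpoints already gives for transfusion. Keep the present analysis with exclusions as a sensitivity analysis.
3. Report bleeding both with the on-enoxaparin limit and regardless of enoxaparin status. Without the second version, retained patients who stop the drug would add to the denominator with few countable events.
4. Report drug interruptions due solely to a renal change separately from minor bleeding. Secondary Endpoints counts interruption by the trauma team as minor bleeding, so retention could otherwise create events that are not bleeds.
5. State that chart-based recording of these outcomes continues after a creatinine trigger. The Consenting section plans contact until discharge, but does not expressly cover patients removed from the study.
6. Report the number triggered by group. Reconcile Level of Risk and Exclusion Criteria on whom the trigger covers, its direction and its reference value.

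The cost is a protocol amendment and continued chart recording for triggered patients. Data Collection already lists the outcomes. Reported bleeding rates may shift slightly in either direction.

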Previous studies have tried to identify predictors for low anti-Xa concentrations. Young age, high body weight, edema, and low peak anti-Xa concentration have been associated with low trough anti-Xa.^{11, 15, 17} AT-III concentrations have not been collected or evaluated in many previous studies. Low AT-III concentrations have not been evaluated as a risk factor for low anti-Xa. Theoretically, low serum AT-III may represent a reduction in substrate to which LMWH can bind and exert anticoagulant effects. Hence, LMWH effectiveness and anti-Xa may be reduced.

Pharmacokinetic / Safety Information

Previous pharmacokinetic studies evaluating enoxaparin prophylaxis and anti-Xa levels suggest high inter-patient variability, especially in critically ill patients (table 1).^{11-12,14} However, the mean maximum serum concentration (C_{max}) did not reach the lower threshold for therapeutic dosing. Therapeutic enoxaparin anti-Xa concentrations are between 0.5 – 1.1 IU/mL for 1 mg/kg every 12 hours, and 1.0 – 2.0 IU/mL for 1.5 mg/kg every 24 hours.¹⁹ No major bleeding events were identified in previous studies.^{12,14} Additionally, evaluation of anti-Xa adjusted dalteparin dosing found no difference in transfusion requirements.¹⁷ Other evaluations of enoxaparin have found few minor bleeding events such as hematoma following total hip arthroplasty, ecchymosis, hematuria, and epistaxis.^{10,20} Based on these previous pharmacokinetic evaluations, patients enrolled in the proposed study would achieve a steady state peak between 0.3 – 0.5 IU/mL and a steady state trough between 0.1 – 0.3 IU/mL. Maintenance of said anti-levels should prevent major bleeding events. Additionally, exclusion of patients with poor renal function, defined as a Cockcroft-Gault calculated creatinine clearance < 30 mL/min will reduce the risk of bleeding events due to reduced drug elimination.

Table 1. Previous pharmacokinetic analyses of enoxaparin.

Trauma Population	Cmax (IU/mL)	Trough (IU/mL)	Half-life (hours)	AUC ₀₋₁₂ (IU/L per hour)	Vd (mL/kg)
Non-Edematous* ¹¹ (30 q12h; n = 11)	0.27 (0.19-0.59)	-	1.67 (0.64-3.92)	1.57 (0.91-3.83)	45.8 (28.9-76.4)
Edematous* ¹¹ (30 q12h; n = 10)	0.12 (0.07-0.34)	-	0.68 (0.31-1.97)	0.63 (0.34-2.18)	43.9 (31.2-68.6)
Rutherford ¹² (40 mg q24h; n = 17)	0.195±0.088	0.044±0.043	-	-	-
Robinson ¹⁴ (40 mg q24h; n = 20)	0.13	-	-	-	-
Robinson ¹⁴ (30 mg q12h; n = 30)	0.15	-	-	-	-
Robinson ¹⁴ (40 mg q12h; n = 40)	0.33	-	-	-	-

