Robinson ¹⁴ (1 mg/kg q24h; n = 19)	0.40	-	-	-	-

Study Justification

Ideal enoxaparin dose for VTE prevention in high-risk trauma patients is unknown. Predictors and explanations for low anti-Xa are also unknown. With emerging evidence demonstrating around 50% of trough anti-Xa concentrations are subtherapeutic and associated with increased VTE risk, the purpose of this study is to compare AT-III serum concentrations as a predictor of low anti-Xa. Secondly, the study will compare two enoxaparin dosing. Ultimately, this information can be used to develop an optimum protocol for patient-specific enoxaparin dosing for VTE prevention to improve patient outcomes.

METHODS**Study design**

This is an investigator-initiated, single-center, prospective, non-blinded, randomized controlled trial. Multi-system trauma patients between 18-80 years old admitted to the University of Cincinnati Medical Center (UCMC), an urban American College of Surgeons-verified Level 1 trauma center will be identified by the Trauma Surgery team. The trauma team will inform study personnel of these patients once enoxaparin is initiated. These patients will be screened for inclusion in the study. Patients who meet inclusion criteria will be administered informed consent by study personnel in their rooms. Patients in the surgical intensive care unit (SICU) and on the surgical floor are eligible for enrollment if all other inclusion and exclusion criteria are met. Informed consent will be obtained prior to enrollment. Goal enrollment is 200 patients with 100 patients in the control group and 50 patients in each randomization group.

Research data collection/study procedures

Patients will be screened daily by the trauma team. Research personnel will be alerted to potential patients for enrollment.

Intervention

Serum AT-III and anti-Xa will be drawn eight hours after the third dose of enoxaparin 30 mg q12h. Serum assays after at least the third dose should approximate drug steady state trough concentrations. Patients with a serum anti-Xa ≥ 0.1 IU/mL will remain on enoxaparin 30 mg every 12 hours and will be the control group. Patients with undetectable anti-Xa (intervention groups), defined as a trough anti-Xa < 0.1 IU/mL, will be randomized to receive either:

- a. Enoxaparin 40 mg every 12 hours (group 1)
- b. Enoxaparin 30 mg every eight hours (group 2)

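### Primary endpoint 2 (goal anti-Xa, group 1 vs group 2) is tested without covariate adjustment although likely predictors are known before randomisation: a missed efficiency, not an error

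*Combined protocol and SAP*

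**What the plan says.** Primary Endpoints, item 2, compares the proportion reaching goal anti-Xa between groups 1 and 2 overall, at the first repeat assessment and at the second. The Data Analysis section gives one rule for all such data: "Hypothesis testing for nominal data will be performed using the Fisher's exact test or chi square test as required based on sample size". It adds "A p-value < 0.05 will designate statistical significance". No covariate-adjusted treatment comparison is described. The Randomization section and the enrollment figure describe 1:1 block randomisation and mention no stratification.

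The only regression is the multivariate logistic model for risk factors of low anti-Xa, where "Serum AT-III, weight, and age will be forced into the model, regardless of p-value". The Background reports that "Young age, high body weight, edema, and low peak anti-Xa concentration have been associated with low trough anti-Xa".

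The sample size rests on the hypothesis that "there will be an absolute difference of 27% in the proportion of patients who achieve goal anti-Xa" between the two groups, "assuming 50% of group 1 achieves goal". Study design states: "Goal enrollment is 200 patients with 100 patients in the control group and 50 patients in each randomization group".

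**The concern.** Two fixed-dose regimens are compared in patients who may weigh anywhere from 50 to 150 kg, and earlier studies link age and weight to trough anti-Xa. If such variables predict attainment, an unadjusted test leaves their variation in the noise, and an adjusted test has more power for the same patients.

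The plan has these variables in hand. Age and weight are eligibility criteria, so they are known at screening. AT-III is drawn with the anti-Xa that decides who is randomised. The plan fixes all three in advance for a secondary question and leaves them out of a primary one.

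The stake is modest but real. Power for this endpoint sits about one point above its 80% target with every patient evaluable, and no dropout allowance is stated.

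**Working it through.** **Inputs.** From Data Analysis and Table 2: 50% vs 77%, alpha 0.05, 80% power, stated total 100. From Study design: 50 per arm. Two-sided testing is assumed, since the sidedness is not stated; it reproduces the table.

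**1. The plan's own figure.** Pooled-variance formula, no continuity correction:

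n per arm = [1.96·√(2·p̄·q̄) + 0.8416·√(p1q1 + p2q2)]² / d²

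- p̄ = (0.50 + 0.77)/2 = 0.635, so √(2 × 0.635 × 0.365) = 0.681
- √(0.50 × 0.50 + 0.77 × 0.23) = √0.4271 = 0.6535
- n = (1.334 + 0.550)² / 0.27² = 3.551/0.0729 = 48.7, so 49 per arm and 98 in total, against 100 stated

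The other four rows of that block reproduce exactly (116, 164, 398, 588). The sample size is sound.

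**2. Power of the planned test at 50 per arm.** z = (0.27·√50 − 1.334)/0.6535 = 0.879, so power is 81.0%. Exact enumeration gives 81.3% for chi-square and 75.3% for Fisher. The smallest expected cell count is 50 × (1 − 0.635) = 18.25, so a rule based on sample size points to chi-square.

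**3. What adjustment could add: approximation.** If baseline covariates explain a share R² of the observed outcome variance, the effective n is 50/(1 − R²). R² is an assumption.

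| R² (observed outcome) | Effective n per arm | Power |
|---|---|---|
| 0 | 50.0 | 81.0% |
| 0.05 | 52.6 | 83.0% |
| 0.10 | 55.6 | 85.0% |
| 0.15 | 58.8 | 87.0% |

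**4. Simulation with three covariates.** 50 per arm, 50% vs 77%, 4,000 trials per setting, logistic likelihood-ratio test. The share here is of the latent (continuous) variable. It runs higher than R² of the yes/no outcome: in a separate logistic simulation, a covariate SD of 1.0 is a latent share of 1/(1 + 3.29) = 23% but an observed R² of 15.8%.

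| Latent share | Chi-square power | Adjusted power | Difference (points) | Adjusted type I error |
|---|---|---|---|---|
| 0 | 80.4% | 80.3% | −0.1 | 5.0% |
| 0.05 | 81.1% | 82.5% | 1.4 | 5.4% |
| 0.10 | 80.7% | 83.3% | 2.6 | 5.1% |
| 0.20 | 82.1% | 86.7% | 4.6 | 5.7% |

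Simulation error is about √(0.81 × 0.19/4000) = 0.6 points on each power and 0.3 points on each type I error. Chi-square's own type I error ran at 5.0–5.6%. A single-covariate simulation gave 87% vs 81% at a 20% share, which sets the upper end of 6 points.

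**5. Effect of selection.** Everyone randomised has already had anti-Xa below 0.1 IU/mL, which narrows the range of anything related to it. With a normal latent trough, selection below the median (the plan's 50% assumption) and an assumed within-patient correlation of 0.5–0.9, a share of 10% in all patients becomes 4–6% among those randomised, and 20% becomes 9–13%. By the table in step 4, that is a gain of roughly 1 to 3 points.

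**6. Number of covariates and variance method.** Expected non-attainers number 25 + 11.5 = 36.5, or about 9 for each of four coefficients (group plus three covariates). With four covariates, one set of simulations gave model-based type I error of 5.7–6.8% (chi-square 5.3–5.7%). A linear model with HC3 standard errors had power of only 77.4% at R² = 0 and 79.5% at R² = 0.05. So the covariates should be few and the test should be named.

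**The case against.** The strongest reply is that nothing is wrong. An unadjusted test of a 1:1 randomised comparison is valid, it matches the basis of the sample size, and it reaches the target in a study that calls itself a pilot. That stands, and it is why this is an improvement and not a correction.

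Four stronger readings are tempting, and the documents do not support them.

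- **That the plan says these variables drive anti-Xa.** It reports associations from earlier studies. Study Justification calls the predictors unknown, and the Background says low AT-III has not been evaluated as a risk factor.
- **That chance imbalance biases the result.** The 5% error rate of the unadjusted test already allows for it. Adjustment improves precision; it does not remove a bias.
- **That adjustment costs nothing.** With several weak covariates or a conservative variance estimator, power can fall below that of the chi-square (step 6). With three covariates and a likelihood-ratio test, the loss at zero share was 0.1 points, within simulation error.
- **That the endpoint is underpowered because Fisher's test gives 75.3%.** The wording permits Fisher, but the expected counts point to chi-square.

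The size of the gain is also fairly disputed. It rests on a share the documents do not give, and selection on low anti-Xa probably shrinks it. This moves the likely gain down but does not remove the case for a change this cheap.

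**Conclusion.** The point holds as a missed efficiency. Primary endpoint 2 is analysed without baseline predictors that the plan collects before randomisation and pre-specifies elsewhere. The planned chi-square is valid and has about 81% power at 50 per arm, so neither the sample size nor the validity of the test is in question.

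The gain from adjustment is about 0 to 6 points of power for a latent share of 0–20% among randomised patients, with the lower part more likely. Three assumptions carry this: the share itself, true proportions of 50% and 77%, and 50 evaluable patients per arm. The documents do not say to which of the three assessments the 27-point difference applies, so the figures hold for any assessment where those proportions hold. Confidence is high that the analysis is unadjusted and moderate at best on the size of the gain.

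**What to change.** For primary endpoint 2, at each stated assessment (overall, first repeat, second repeat), specify before outcome data are examined:

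- a logistic regression of attainment on randomised group, adjusted for age, weight and AT-III at assay #1, with the group effect tested by likelihood ratio
- the standardised difference in proportions with a bootstrap 95% CI as the reported estimate
- the unadjusted chi-square as a supportive analysis
- covariates fixed in advance: no p < 0.2 screen, and no post-randomisation values such as peak anti-Xa or serial AT-III
- simple imputation of any missing baseline covariate, for example the mean over all randomised patients, so that nobody randomised is dropped.

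This changes SAP wording only and needs no extra patients or blood draws. The costs are slightly more analysis work, a negligible loss of power if the covariates prove uninformative, and an odds ratio that is conditional on the covariates. The standardised risk difference deals with the last of these.
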